Subjects for this study will be recruited from those patients referred for diagnostic EUS FNA of solid pancreatic lesions by a physician responsible for their care (i.e. gastroenterologists, oncologists, general internists, and surgeons) to the principal investigator or co-investigator / collaborators as per standard practice.

5. Study Procedures

Data to be Collected, Study Visits and Parameters Measured.

Demographic data:

Demographic related data will be collected from the subject, medical records and the referring physician. This includes age, gender, co-morbid illnesses, type of cancer, tumor location, presence of metastases, method of diagnosis, therapy to date, laboratory results, relevant imaging studies and reports.

Procedural data:

Procedural related data will also be recorded from procedure report such as lesion location, lesion size, echogenic features of lesion, number of FNA passes performed, site of FNA (i.e. transduodenal or transgastric), type and sequence of needle used, use of stylet, use of suction, cytologic and histologic diagnosis.

Immediate outcomes:

Immediate outcomes to be assessed are adequacy of specimen obtained for cytologic and histologic diagnosis. Adequacy of the specimen will be determined by review of cellular/tissue material obtained by a cytologist/pathologist for each needle pass that is taken. See appendix E & F for representative analysis. Any procedure-related complications related to the FNA will be recorded.

Medications:

Subjects will not receive or be exposed to any additional medications as a result of participation in this study. Subjects will receive sedation for endoscopic procedures as this is standard practice and as would be administered regardless of participation in the study. Patient will have an intravenous line placed for administration of sedation prior to the procedure as is standard practice. Anesthesia will sedate and monitor all patients referred for EUS FNA procedures in accordance with our endoscopy unit practice. The duration of the procedure and length of sedation period is not expected to be any longer than would otherwise be required. The patient will sign a separate consent for sedation.

Devices (see device package inserts):

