The 22-gauge core biopsy needle with reverse bevel design (EchoTip® Procore™) will be compared prospectively to the standard straight hollow-core 22-gauge or 25-gauge FNA needle already used in our clinical practice for the diagnosis of solid pancreatic lesions. The needles to be used in this study are FDA-approved, commercially available and currently in use at MDACC.

EUS FNA 22/25-gauge Needle	EUS FNA 22-gauge Needle
Straight Hollow-Core Needle	Reverse Bevel Design
Collect only Cells	Collect Cells and Tissue

Interventions:

Patients who are referred for EUS guided FNA and who consent to participate will have their examination performed using two different needles. As part of the study two passes will be performed with the standard 22-gauge or 25-gauge straight hollow core needle and two passes will be

performed using the 22-gauge EchoTip® Procore™ needle. All passes will be taken from a single lesion and from the same endoscopic location. All passes will be numbered. Both passes taken with the standard needle will be sent for immediate cytologic evaluation as is standard. One of the 22-gauge EchoTip® Procore™ passes will be sent for immediate cytologic evaluation and one pass will be sent for histology. Additional non-study passes will be obtained if necessary (after immediate cytologic evaluation of the three initial passes) using needle of endoscopist's choice. If adequate sampling is believed to have been obtained in fewer than 4 total passes as confirmed by immediate cytologic assessment then no additional passes need be performed at the discretion of the endoscopist and analysis will be performed with existing data. All other elements of the exam will be otherwise unchanged. The endoscopist performing the procedure will alternate the sequence of EUS needles used in any given patient. In addition we will alternate which Procore™ pass is sent for histology and cytology. The primary intervention will be which needle is used and in which sequence. The reason for alternating sequence is to eliminate any confounding variable associated with sequence such as increased bloody aspirate or possible variability in cytologic yield related to increased number of passes. The study does not involve an increased or excessive number of passes or other additional interventions beyond what would be current standard practice. This procedure will be explained to subjects at time of consent.

Cytopathologic Evaluation:

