possible). Any additional passes will not be included in the study. The need for additional passes will be determined based on the three passes (two straight hollow-core standard FNA needle and one EchoTip® Procore™ needle) sent for immediate cytologic assessment during the procedure as is routine at our center. Immediate assessment is not possible for the one pass submitted for histologic analysis with the EchoTip® Procore™. Each needle pass submitted for review will be rated individually by the cytologist/pathologist (see appendix E & F for cytopathology rating sheet as applicable). A final analysis will be performed on the diagnostic results from each needle pass. For the purpose of the study, if the passes are adequate to be diagnostic, the result will be considered “yes”. If the passes are inadequate, the result will be considered “no”. Equal number of biopsies will be taken for each needle sequence.

Power and Sample Size:

The two standard straight hollow-core FNA passes are assumed to be diagnostic in 65% of patients. The two Procore™ needle passes are assumed to be diagnostic in 85% of patients. Assuming a discordant proportion of 30%, a sample size of 60 patients will be needed to achieve 80% at a 5% significance level.

For the comparison, McNemar's test will be used for the sample size justification. Our null and alternative hypotheses are:

$$H_0: P_a - P_b = 0 \text{ vs. } H_a: P_a - P_b \neq 0$$

Where P_a and P_b are the diagnostic proportions for the 22-gauge EchoTip® Procore™ needle and standard 22-gauge or 25-gauge straight hollow core needle respectively.

Table 1 displays in the scenario the sample sizes needed to achieve about 80% power with a two-sided significance level of 0.05 for different scenarios with different assumptions for proportion discordant.

Sample size	Difference in positive proportions	Proportion Discordant	power
60	0.2	0.3	0.8

In this study, we assume that the 22-gauge EchoTip® Procore™ needle will have a higher diagnostic yield (85%) than a standard straight hollow-core FNA needle after two passes (65%). A sample size of 60 patients will achieve about 80% power at a 5% significance level using a two-sided inequivalence test of correlated proportions when it is assumed that there is 20% difference regarding biopsy result (positive vs. negative) and the discordant proportion is 30%.

Statistical Analysis:

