Data analysis will be performed using SAS as appropriate. Intent-to-treat data will be used for primary analysis. Demographic and disease characteristics of the patients at registration will be summarized using descriptive statistics such as mean, standard deviation (SD), median and range. Biopsy result (diagnostic proportion) from each needle type will be presented with 95% confidence intervals. McNemar test will be used to compare diagnostic ability (yes vs. no) between the two pass information obtained from the standard straight hollow-core needle (22-gauge or 25-gauge) and the one pass information obtained from the 22-gauge EchoTip® Procore™ needle. In addition, McNemar test will be used to compare diagnostic ability (yes vs. no) between either of the two pass information obtained from the standard straight hollow-core needle (22-gauge or 25-gauge) and the one pass information obtained from the 22-gauge EchoTip® Procore™ needle.

Demographics and Other Characteristics:

Summary statistics for patients' demographics and other characteristics will be presented descriptively.

Primary Endpoint:

Comparison of a diagnostic cytopathology specimen provided from FNA of a solid pancreatic lesion using the two different needles as determined by a cytologists who will be blinded to needle type and sequence.

Secondary Endpoint:

Assessment of adequate specimen for histologic diagnosis with Procore™ needle of a solid pancreatic lesion. Comparison of cytological diagnosis from both needle types with histological assessment of Procore™ needle specimen.

7. Risks and Discomforts

There is not expected to be any increased risk with use of either needle above and beyond what is standard for the procedure. Both needles used in the study are already FDA approved, commercially available and used in clinical practice, including here at MD Anderson. Both needles are similar in size. There is no increased number of passes performed as part of this study. In addition it would not be possible to determine any specific procedure related complication to use of one needle verses the other in the setting of this study. We will keep track of the overall frequency of adverse events that are standard to the procedure.

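### The planned McNemar tests ignore the recorded needle order: little is lost if the two orders stay equal, but type I error rises if the evaluable pairs become unbalanced

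*Combined protocol and SAP*

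**What the plan says.** In the combined protocol and SAP, section 5 (Interventions) has both needles sample one lesion from one endoscopic position, with the endoscopist alternating the needle sequence. The stated purpose is: "The reason for alternating sequence is to eliminate any confounding variable associated with sequence such as increased bloody aspirate". The same sentence also names yield changing as passes accumulate. Section 6 (Study design) adds: "Equal number of biopsies will be taken for each needle sequence". Section 5 (Procedural data) lists the items recorded, including "type and sequence of needle used, use of stylet, use of suction".

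Section 6 (Statistical Analysis) then plans: "McNemar test will be used to compare diagnostic ability (yes vs. no) between the two pass information obtained from the standard straight hollow-core needle" and the one-pass Procore result. A second McNemar comparison sets either of the two standard passes against the same Procore result. Neither has an order term, stratification by order or an order sensitivity analysis, and no other section uses the recorded sequence.

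Section 5 (Interventions) also lets the endoscopist stop before four passes once on-site cytology is judged adequate. The analysis then uses whatever was collected.

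**The concern.** This is in effect a two-sequence crossover within a lesion: the second needle meets tissue that the first has already disturbed. The protocol expects this to matter and balances it by design, but the analysis discards the information that would show whether it did. Three things are at stake:

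- some power, because variation due to order is left in the comparison;
- the type I error, if the two orders are not equally represented among evaluable pairs;
- any report of whether the anticipated order effect occurred.

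**Working it through.** **1. Inputs and the plan's own figure.** Section 6 (Power and Sample Size) aims for "about 80% power with a two-sided significance level of 0.05". For the standard needle it says: "The two standard straight hollow-core FNA passes are assumed to be diagnostic in 65% of patients". The matching Procore yield is put at 85%, a difference of 20 points. The sample size statement reads: "Assuming a discordant proportion of 30%, a sample size of 60 patients will be needed to achieve 80% at a 5% significance level". The discordant cells therefore satisfy p10 + p01 = 0.30 and p10 − p01 = 0.20, so p10 = 0.25 and p01 = 0.05. Power was summed over the number of discordant pairs, Binomial(60, 0.30), with each pair favouring Procore with probability 0.25/0.30. Exact McNemar gives 79.7%, which reproduces the stated 80%. The uncorrected chi-square version gives 85.7%. The plan does not say which version it will use, so both are shown.

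**2. What equal orders achieve.** Read the plan as two groups, Procore first (n1) and standard first (n2). Let D be the true needle difference and δ the loss of yield from going second, the same for both needles. The expected within-patient difference (Procore minus standard) is D + δ in the first group and D − δ in the second. The pooled difference has expectation

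D + δ(n1 − n2)/(n1 + n2).

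At 30:30 the second term is zero. With δ = 15 points it is 15 × 10/60 = 2.5 points at 35:25 and 15 × 20/60 = 5.0 points at 40:20.

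**3. What pooling leaves in the variance.** At 30:30 the pooled variance of a within-patient difference is (discordant proportion) − D². The within-order variance is smaller by δ². In a random-intercept logistic model calibrated to 85%, 65% and 30%, with average yields held fixed as δ grows, the discordant proportion is 0.313 at δ = 12 points and 0.346 at δ = 23 points:

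- δ = 0: 0.300 − 0.040 = 0.260
- δ = 0.120: 0.313 − 0.040 = 0.273 pooled; 0.273 − 0.014 = 0.259 within order
- δ = 0.231: 0.346 − 0.040 = 0.306 pooled; 0.306 − 0.053 = 0.253 within order

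**4. Power at 30:30 (outcomes enumerated).** The order-adjusted estimate is (d1 + d2)/2, where d1 and d2 are the mean within-patient differences in the two order groups. Its standard error is √[s²(1/n1 + 1/n2)/4], with s² the pooled within-group variance, referred to t on n1 + n2 − 2 = 58 degrees of freedom.

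| Assumed order effect | McNemar, chi-square | McNemar, exact | Mainland-Gart | Order-adjusted difference |
|---|---|---|---|---|
| 0 points | 85.7% | 79.7% | 85.8% | 85.8% |
| 12 points | 84.6% | 78.1% | 82.3% | 85.8% |
| 23 points | 81.6% | 73.4% | 70.3% | 85.6% |

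Against the order-adjusted difference, chi-square McNemar loses 85.8 − 84.6 = 1.2 points and 85.6 − 81.6 = 4.0 points. Exact McNemar falls below its own no-order value by 79.7 − 78.1 = 1.6 points and 79.7 − 73.4 = 6.3 points.

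**5. Type I error.** Here there is no needle difference: both average 75% with 30% discordant before an order effect is added. The assumed order effect is 15 points (82.4% when first, 67.6% when second).

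| Evaluable orders | McNemar, chi-square | McNemar, exact | Order-adjusted difference |
|---|---|---|---|
| 30:30 | 4.4% | 2.4% | 5.0% |
| 32:28 | 4.6% | 2.6% | 4.9% |
| 35:25 | 5.7% | 3.3% | 5.0% |
| 40:20 | 9.7% | 6.1% | 4.9% |

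With a 28-point effect, chi-square McNemar gives 3.0% at 30:30, 6.8% at 35:25 and 20.0% at 40:20. The order-adjusted test stays near 5% throughout.

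**6. Carry-over specific to one needle.** Suppose there is no true difference, orders are 30:30, and only one needle loses yield when used second (75.0% to 66.9%, about 8 points). The bias is half of that, 4.1 points. Type I error is 8.8% pooled and 8.7% after order adjustment, so adjustment does not help.

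**The case against.** The strongest reply is that the design already deals with order. If each endoscopist alternates as written, each adds an imbalance of at most one patient, so 40:20 is far from the plan. With equal orders the test errs on the safe side. This stands, and it limits the point.

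A reader might infer that the primary result, as planned, mixes the needle effect with the order effect. Step 2 shows that it does not at equal orders when the effect is common to both needles. Nor does the protocol claim that alternation has succeeded in removing confounding; it states a purpose.

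A reader might also infer a large power loss. If order is modelled as a shift in the log-odds among discordant pairs, with discordance fixed at 30% and needle odds of 5:1, pooled power falls from 86% to about 80% and 71% for order odds ratios of 2 and 3. But that model shrinks the needle difference itself:

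- ratio 2: odds of 10 and 2.5 average to a probability of 0.812, a difference of 0.30 × (2 × 0.812 − 1) = 18.7 points;
- ratio 3: odds of 15 and 1.67 average to 0.781, a difference of 16.9 points.

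With those smaller differences and no order effect, power is already 80.0% and 70.1%. The fall is therefore not a cost of pooling.

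What the reply does not cover is the stopping rule in section 5 (Interventions). Skipped passes are the later ones, so pairs can be lost more often in one order than in the other even if assignment is 30:30. The documents do not say how often this will happen.

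**Conclusion.** The plan collects needle order, expects it to matter and leaves it out of the analysis. As designed, with equal orders, the cost is small: about 1 to 4 points of power for order effects of 12 to 23 points, or about 2 to 6 with the exact test. The test remains valid. Inflation of type I error needs unequal evaluable orders and is small until about 35:25. At 40:20 with a 15-point effect it reaches 9.7% (6.1% exact), against 4.9% after adjustment.

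All order effects and splits are assumptions. The power figures also take the plan's 85%, 65% and 30% as given. This is a worthwhile, inexpensive improvement, not an error that invalidates the primary test. The documents do not support saying that the planned comparison is biased by a common order effect, or that order adjustment would cure carry-over.

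**What to change.** In section 6 (Statistical Analysis):

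1. Make the primary comparison an order-adjusted paired difference: the within-patient difference averaged with equal weight over the two needle-order groups, using the within-group variance. This is the intercept of a linear regression of the difference (−1, 0, +1) on order coded −½ and +½.
2. Report the estimated order effect, (d1 − d2)/2, with its confidence interval, and the number of evaluable pairs in each order.
3. Keep McNemar as a sensitivity analysis, and state whether it is exact or chi-square. Do not make Mainland-Gart primary: it uses only discordant pairs and here has less power than chi-square McNemar (82.3% v 84.6% at 12 points, 70.3% v 81.6% at 23).
4. Add a comparison of first-used needles only, as a check on needle-specific carry-over. It is imprecise: with 30 per group at 85% and 65%, the standard error is √(0.85 × 0.15/30 + 0.65 × 0.35/30) = 0.109, so the 95% interval is about ±21 points.

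The cost is wording only, since the sequence is already recorded and no extra patients are needed. The downside arises if orders end up unequal and there is no order effect. At 40:20 the variance factor is (1/40 + 1/20)/4 = 0.01875 against 1/60 = 0.01667, and power is about 81% against 86% for chi-square McNemar.

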The specimens are to be assessed independently by members of the MDACC cytology/pathology department who will be blinded to the needle sequence and type of needle used. For the purposes of the study cytopathologic results will be recorded from the slides of each of the numbered individual passes taken. Reports for immediate assessment purposes will be based on the 3 passes sent to cytology and any additional passes required outside the study including the cellblock made from wash of all needle passes. The cytological specimen quality will be graded on cellularity and other features

comparable to the assessment in our earlier study by Lee et al. (10) (see Appendix E & F). The single Procore™ sample sent to histology will be processed like any other endoscopic biopsy specimen (immediate assessment not possible as with cytology due to processing requirements) and the final pathology report will be used for comparison purposes to the cytological specimen results.

Study Duration:

The expected duration of the study is approximately 2 years from the commencement of subject enrollment. Subject enrollment is expected to be up to one year. All subjects will be followed until surgery, death, or at least six months until last subject enrolled.

6. Biostatistical Analysis

Study design

The primary objective of the study is to assess if the 22-gauge EchoTip® Procore™ needle has a better diagnostic performance compared to standard 22-gauge and 25-gauge straight hollow core needles (both 22-gauge and 25-gauge needles are used interchangeably). The primary endpoint is whether or not the needle pass result provides diagnostic material (yes vs. no). For each patient, both needles will be used to sample the same lesion. Two needle passes will be performed with each needle type. The average number of needle passes needed to obtain a diagnostic specimen of solid lesions in the pancreas is four using the standard 22-gauge or 25-gauge straight hollow core needle in our practice (although the number of passes can be variable in any given lesion for a variety of reasons). All needle passes will be numbered and evaluated individually. For the two passes taken from the straight hollow-core standard-needle, the specimens are to be assessed by cytology for immediate review. For the two passes taken with the EchoTip® Procore™ needle, one pass will be submitted to cytology for immediate review and one pass for pathology (immediate review not

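### No planned test compares per-pass cytologic yield using both standard passes together, although all three cytology passes are rated individually

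*Combined protocol and SAP*

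**What the plan says.** Section 6, Study design, defines the endpoint at pass level: "The primary endpoint is whether or not the needle pass result provides diagnostic material (yes vs. no". It adds that "Each needle pass submitted for review will be rated individually by the cytologist/pathologist", and promises a final analysis of the results from each pass without naming a method. Section 5, Interventions, sends both standard passes and one Procore pass to cytology; the other Procore pass goes to histology. The same section lets passes be left out, at the endoscopist's discretion, once immediate cytology shows adequate sampling, and the data in hand are then analysed.

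Section 6, Statistical Analysis, names two McNemar tests. The first compares the two-pass standard result with one Procore pass. The second, introduced as an addition, is "between either of the two pass information obtained from the standard straight hollow-core needle" and one Procore pass.

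The sample size rests on a different contrast, two passes against two: "The two standard straight hollow-core FNA passes are assumed to be diagnostic in 65% of patients" and "The two Procore™ needle passes are assumed to be diagnostic in 85% of patients".

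**The concern.** The per-pass comparison gives each needle the same number of attempts, so it is the like-for-like one. McNemar's test takes one result per needle per patient, so with two standard passes and one Procore pass the plan must say how the second standard rating enters. It does not. At stake are precision from ratings already being collected, and an answer that could depend on which standard pass is used.

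**Working it through.** **1. The plan's own figure.** Inputs from section 6, Power and Sample Size: difference d = 0.85 − 0.65 = 0.20, discordant proportion D = 0.30, N = 60, two-sided 0.05. The usual normal approximation gives power Φ[(d√N − 1.96√D)/√(D − d²)] = Φ[(1.549 − 1.074)/0.510] = 82.5%. The exact McNemar test gives 79.7%. The stated power of about 80% reproduces for two passes against two.

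**2. The readings of *either*.**
- One chosen standard pass: the other is unused.
- Each pass in turn: both are used, but in two tests with no rule for combining them. In the simulations of step 5 with a common correlation, the two exact tests reached different verdicts in 31% to 34% of trials.
- At least one diagnostic: two attempts against one, as in the first planned test.

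**3. Precision from the second standard pass.** Let D_PS be the probability that Procore and a standard pass disagree, D_SS the probability that the two standard passes disagree, and d now the per-pass difference in yield. Per patient:
- Procore minus one standard pass: V1 = D_PS − d²
- Procore minus the mean of both: V2 = V1 − D_SS/4

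The one-pass test needs 60 × V1/V2 patients to match 60 patients analysed with both passes. With equal yields and one common correlation, D_PS = D_SS and d = 0, so V2/V1 = 0.75 and 60/0.75 = 80.

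Per-pass yields can be backed out of the 65% and 85% figures. With independent passes they are 1 − √0.35 = 0.408 and 1 − √0.15 = 0.613, giving V1 = 0.479, V2 = 0.358 and an equivalent N of 80. Common correlations up to 0.8 give 80 to 84.

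**4. How far this can move.** The documents give no between-pass correlation. As a wide range, treat 65%, 85% and 30% as if they were per-pass values (they are two-pass figures in the plan). Then V1 = 0.30 − 0.04 = 0.26 and D_SS = 2 × 0.65 × 0.35 × (1 − ρ), where ρ is the correlation between the two standard passes. The equivalent N is 107 at ρ = 0, 92 at 0.2, 77 at 0.5, 69 at 0.7, 63 at 0.9 and 60 at 1. The top of this range is implausible. A 30% discordance implies a Procore–standard correlation of (0.60 − 0.5525)/√(0.2275 × 0.1275) = 0.28, so ρ below that means standard passes agree less with each other than with Procore.

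**5. Same-needle passes more alike.** Assumed model: probit with a lesion effect and a lesion-by-needle effect; 20,000 simulated trials per setting; N = 60. Power uses yields of 0.408 and 0.613. Type I error and equivalent N use 50% for both needles.

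| Latent correlation, between needles / same needle | Equivalent N | Power: McNemar, one standard pass, exact / uncorrected | Power: paired difference, both passes | Type I error: paired difference | Type I error: patient-stratified CMH |
|---|---|---|---|---|---|
| 0 / 0 | 80 | 53% / 62% | 73% | 5.1% | 5.1% |
| 0.2 / 0.2 | 80 | 59% / 68% | 79% | 5.2% | 5.1% |
| 0.4 / 0.4 | 80 | 66% / 75% | 85% | 5.0% | 5.1% |
| 0.2 / 0.4 | 76 | 58% / 68% | 77% | 4.9% | 6.3% |
| 0.2 / 0.6 | 72 | 58% / 68% | 75% | 5.0% | 8.0% |
| 0.4 / 0.8 | 70 | 65% / 74% | 80% | 5.0% | 9.3% |

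The Cochran-Mantel-Haenszel (CMH) column follows from algebra. Under the null the true variance over the variance the test assumes is (4D_PS − D_SS)/(2D_PS + D_SS). In the fourth row this is (4 × 0.436 − 0.369)/(2 × 0.436 + 0.369) = 1.108, so the error is 2[1 − Φ(1.96/√1.108)] = 6.3%.

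**6. Omitted passes.** If the second standard pass is missing at random in 10%, 20%, 30% or 50% of patients, the 20-patient gain falls to about 18, 16, 14 or 10. Omission under section 5 depends on results, which is worse. Assume a 50% yield for both needles, independent passes, and the second standard pass skipped in half of the cases where the first was diagnostic. Averaging whatever is available gives a standard yield of 0.5 × (0.5 × 1 + 0.5 × 0.75) + 0.5 × 0.25 = 0.5625, a bias of about −6 points against Procore when the needles are equal. If always skipped, it is 0.5 × 1 + 0.5 × 0.25 = 0.625, or −12.5 points. Correlated passes give somewhat less.

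**The case against.** McNemar's test on one result per needle is valid, the second test is introduced only as an addition, and N = 60 was justified on another contrast. On this view, choosing a more efficient method is a preference, and defining *either* would be enough. The validity point stands: uncorrected one-against-one McNemar stayed at 5.1% to 5.6% in the null simulations. But a definition alone would settle which reading applies and still leave no combined per-pass comparison, although Study design promises an analysis of each pass.

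Two stronger readings are tempting. A reader might infer that the plan throws away one standard pass. That is true on only one reading of *either*, and the first McNemar test uses both passes. A reader might also infer that the trial is 20 patients short. The documents do not support that: "A sample size of 60 patients will achieve about 80% power at a 5% significance level" reproduces for its stated contrast, and 20 is a precision equivalent under stated conditions, not a correction to the sample size.

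It is also fair to object that the obvious three-pass test, CMH stratified by patient, can exceed its nominal level, and that omitted passes can bias an average. Both objections stand, and they determine the form of the fix.

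**Conclusion.** The gap is real: as written, no single planned test compares per-pass cytologic yield with both standard ratings. Filling it would make 60 patients act like about 80 if yields are similar, the three passes share one correlation and all are taken. The equivalent is about 70 to 76 in the simulated settings where same-needle passes agree more with each other, and 60 if they always agree. Against uncorrected McNemar, power rises by about 6 to 11 percentage points in those simulations. The between-pass correlations and the per-pass yields are assumptions, so the gain should be quoted as a range. It also depends on the second standard pass usually being taken. This is an efficiency and prespecification defect worth correcting; it does not invalidate the planned tests or the sample size.

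**What to change.** Replace the second McNemar sentence in section 6, Statistical Analysis, with text such as:

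> Per-pass cytologic yield will be compared on the three cytology passes. For each patient the difference is the Procore cytology result minus the average of the two standard results (diagnostic = 1, not diagnostic = 0). The mean difference over patients will be given with a 95% confidence interval and tested as a patient-level paired difference at the two-sided 5% level. Omitted passes will be tabulated by needle, sequence and earlier results and handled by [stated method]; the available passes will not simply be averaged. As a sensitivity analysis, the first standard pass will be compared with the Procore cytology pass by McNemar's test.

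GEE with patient-clustered robust variance is an acceptable alternative, but robust variance does not by itself correct for result-dependent omission. Patient-stratified CMH should not be used, because it assumes exchangeable passes.

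For the stated method, one option is multiple imputation from earlier pass results and sequence, with limits that count every omitted pass as diagnostic and then as not diagnostic. If a pass is always omitted after a given result, imputation has nothing to draw on and only the limits are informative.

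The cost is a short paragraph and slightly more analysis work, with no new passes, patients or ratings. The drawback is that the result relies on the second standard pass usually being taken.
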